to ensure the safety of the child, a member of the research team supervised by a mental health professional will contact the participant within 24 hours to follow-up

Finally, all participating families enrolled in the study will be given [name] contact information on the consent/assent forms.

All participant data will be collected via Qualtrics, which meets GSU standards for encryption. GSU has extensive experience safeguarding the security and integrity of sensitive materials, including protected health information and sensitive financial information. Respondent confidentiality will be masked in all data files by the use of project identification numbers rather than personal information. All other electronic records, including digital recordings of sessions, are de-identified in collection and will be maintained in password-protected locations on the secure server. All paper records will be de-identified and maintained in a locked file cabinet on a secure floor. The only document linking participants with identification numbers will be retained in a password-protected encrypted file on the secure server. That linking document will be destroyed at the end of the study. Data presented at professional meetings or published in journals or books will not allow identification of individual participants. These procedures are expected to minimize any potential adverse effects from participating in this study.

7. Benefits

Potential benefits to participants who receive the prevention program are substantial, including decreased likelihood of substance misuse, sexual assault victimization, sexual assault perpetration, and engagement in sexual risk behaviors, thereby decreasing the risk of subsequent development of substance use disorders and sexual revictimization, though these cannot be guaranteed. In addition, the successful demonstration of feasibility for a clinically useful and cost-effective technology-based approach to improve the efficiency, effectiveness, and reach of prevention programs to primary care would be of significant benefit to society. Further, this technology could be adapted to other populations if effective.

8. Compensation

Participants in the pilot feasibility trial will receive:

- A \$5 Walmart e-gift card for completing the screening survey even if they are not eligible or do not finish the study.
- A \$30 Walmart e-gift card for completing the baseline survey
- A \$10 Walmart e-gift card for completing the online prevention program (if randomized to the intervention)
- A \$40 Walmart e-gift card for completing the 1-month follow-up
- A \$45 Walmart e-gift card for completing the 3-month follow-up
- A \$50 Walmart e-gift card for completing the 6-month follow-up
- In addition, participants who complete each survey within a week of the date they were sent the survey will receive an additional \$5 per survey.
- Participants will also receive a \$10 bonus for completing **all** surveys
- Participants may also receive partial payment for the follow-up surveys based on the percentage of the survey they complete.

9. Data Analysis: Data Management & Monitoring

To address electronic data security, Qualtrics at GSU will be used for data collection. Questionnaire data will be collected via software that meets GSU standards for encryption. GSU has extensive experience safeguarding the security and integrity of sensitive materials, including protected health information and sensitive financial information. Respondent confidentiality will be masked in all data files by the use of project identification numbers rather than personal information. All other electronic records, including digital recordings of sessions, are de-identified in collection and will be maintained in password-protected locations on the secure server. All paper records will be de-identified and maintained in a locked file cabinet on a secure floor. The only document linking participants with identification numbers will be retained in an encrypted file on the secure server with access limited to [name] and the research personnel. This linking document will be destroyed at the end of the study. Data presented at professional meetings or published in journals or books will not allow identification of individual participants. These procedures are expected to minimize any potential adverse effects from participating in this study. All final data will be stored on GSU secure servers, on GSU password-protected computers.

10. Plans for Analysis, Statistical and/or Otherwise

Feasibility will be determined based on recruitment, retention, execution of study protocols, and satisfaction of adolescents and providers. Feasibility is the primary goal of this aim. Recruitment will be considered successful if 250 adolescents are screened and 70 meet criteria for the study. Study retention will be considered successful if 80% of participants are retained for 1-, 3-, and 6-month follow-up assessments. Satisfaction will be considered adequate if participants report at least average satisfaction with the prevention program. Feasibility will be used to inform a larger randomized clinical trial. Preliminary effects: Preliminary effects will be examined as a secondary goal to determine preliminary evidence of effects on substance use, SA victimization, SA perpetration, and SRBs. The small sample size prevents any conclusions regarding prevention program efficacy to be determined, however, ANOVAs (gender X treatment

condition) will be conducted to determine if there are any preliminary effects on substance use, SA victimization, SA perpetration, and SRBs. Given that the primary aim is to determine feasibility and not to determine effects on outcomes, this will be preliminarily examined.

11. Training of Study Team

All study staff will be approved by all involved IRBs and will receive extensive training from the grant PI ([name]) on study procedures and risk protocols. Specifically, study staff will receive training on suicide risk assessment and suicide risk management as well as on assessing for child safety in relation to sexual assault histories. All investigators and study staff will complete the required CITI training and study staff with direct contact with participants will have weekly supervision meetings as well as 24-7 access to [name], a licensed clinical psychologist, for any study-related concerns.

12. Plans for Monitoring the Study for Safety

[name] will be responsible for monitoring the safety and efficacy of this trial, executing the NIDA- approved Data and Safety Monitoring (DSM) plan, and complying with the reporting requirements. [name] will provide a summary of the DSM report to NIDA on an annual basis as part of the progress report. The DSM report will include the participants' socio-demographic characteristics, expected versus actual recruitment rates, any quality assurance or regulatory issues that occurred during the past year, summary of adverse events, and any actions or changes with respect to the protocol. The DSM report to NIDA will also include, when available, the results of any data analyses.

A. Participant Safety

Diligent safety monitoring will be conducted by the candidate throughout this study in compliance with the following required elements of the GSU IRB and continuing review process:

1. tracking of subject accrual (enrollment, drop-outs, demographics)
2. timely and appropriate reporting of informed consent process deficiencies, protocol deviations, privacy breaches, conflicts of interest, and/or changes in personnel
3. ongoing monitoring and appropriate reporting of adverse event activity: a. Internal: i) frequency of unexpected, related or possibly related, and serious or more prevalent than expected adverse events; ii) frequency of internal deaths occurring during the study or within 30 days of study termination, even if expected or unrelated b. External: frequency of unexpected, related or possibly related, and serious adverse events
4. interim assessment of risk/benefit relationship in reference to adverse event occurrences, preliminary observations, and emerging information
5. timely and appropriate IRB submission of safety-related documents such as audit reports, sponsor progress reports, and other materials or communications that might impact the safe conduct of this study
6. active cooperation with the IRB and other applicable entities in the event of a random or for-cause internal or external audit

Participant Safety Relevant to Specific Application. Regarding the risk of harm to self or others, the nature of the population (adolescents at risk for using substances, SA, and SRBs) entail that specific adverse events, such as suicidal and homicidal ideation and

attempts, are possible given the high-risk nature of the population under study. Regardless, both expected adverse events and unexpected adverse events will be monitored and addressed continuously throughout the course of the project. Risk of harm to self and others will be directly assessed through self-report questionnaires. Participants in the study who indicate any risk of harm will immediately be assessed and referred for treatment, if needed. [name] and her mentorship team have extensive training in crisis management. [name] was directly clinically trained by [name], the developer of Dialectical Behavior Therapy which is effective at reducing suicidal behavior. Therefore, she is well versed and very experienced in the assessment and management of acutely suicidal individuals. Both expected and unanticipated adverse events will also be continuously monitored by the candidate and mentorship team. All study staff will be closely supervised by the candidate, who will hold weekly meetings with the staff to address clinical barriers, prevention program and enrollment progress, and safety issues throughout the feasibility trial. [name] will also be available 24/7 to study staff by phone if any additional support is needed. Participant safety is assessed routinely as part of the research context through assessments given at each time point to evaluate substance use, SA, SRBs, and risk of harm.

For participants enrolled in the study, in any circumstances where the study staff is concerned regarding suicidal or homicidal ideation or attempt, or SA perpetration against a minor, s/he will immediately contact [name], who is a licensed psychologist in South Carolina (License No. PSY.1417). [name] will assess safety and provide instructions to the study staff to address any risks. [name] will ensure that the study staff are well-trained in assessing distress and suicidality (ideation, intent, plan, etc). In circumstances where participants express suicidal ideation and are sincerely willing to contract for safety (i.e., will agree to keep her/himself safe), a plan will be made and carefully monitored. If a participant is deemed at-risk for suicide and will not contract for safety or has made a suicidal behavior or attempt, the participant will be assessed by a local emergency department for possible inpatient hospitalization. [name] or trained research staff will also ensure that participants who present with risk for suicidal or homicidal ideation are well educated on how to access 24-hour emergency care (through 9-1-1 or going to the local Emergency Department). [name] will be on-call for study therapists, 24 hours per day, 7 days per week.

B. Procedures for Monitoring Safety of Data

Regarding data management and storage, all data will be collected using computerized self-report questionnaires. Only participants' study identification codes will be inputted computer-based databases. The codes that link the name of the participant and the study ID will be kept confidential by [name] in a secured cabinet. The data will be imported directly into a password-protected SPSS data file stored on the GSU server. The server is protected by the GSU network, and a secured log-in is required from all users. All research personnel collecting and manipulating data will have completed a Human Subjects Research Training and will meet weekly with [name] or a postdoctoral fellow in the lab to ensure strict compliance with the DSM plan. Only study personnel (candidate, research staff, and mentorship team) will have access to data. No data will be released to other agencies unless participants consent to release.

Adverse Events

The candidate, with consultation from the mentoring team—which includes a licensed clinical psychologist ([name])—will be responsible for monitoring data and participant safety. Adverse events will be one of the standard agenda items during weekly research meetings. Any adverse event that occurs will be reported by [name] to the GSU IRB, as well as NIDA. In keeping with the IRB requirements, events that are not considered severe are reported to the IRB in writing no later than 10 working days after the Investigator learns of the event, whereas those that are severe will be reported immediately and no longer than 48 hours after learning of the event. If instances arise where the severity of the event is questionable to the candidate, the IRB official assigned to the protocol will be contacted for guidance. In addition to reporting the adverse event to the IRB, those events that involve maltreatment of a child or risk of harm will be reported to appropriate child protection and law enforcement agencies. All reported events and any action taken by the IRB will be reported to the NIH.

Adverse Identification, Detection, Grading, Attribution, and Reporting

1. **Identification.** Potential risks identified for participants will be listed in the IRB-approved informed consent document. Additional unknown risks might occur and, if so, will be identified through diligent investigator monitoring throughout the conduct of this study.
2. **Detection.** During the informed consent process, participants will be advised of the potential risks of participation as identified in the IRB-approved informed consent document. Participants will be advised during the informed consent process that they should promptly inform the investigators of any concerns regarding adverse events related to participation in the study. Participants will be advised to notify [name] of any suspected adverse events in a timely fashion. Safety parameters will be followed by the candidate as outlined above.
3. **Grading.** Adverse events will be assessed and graded as follows:
 1. Expected/Anticipated Adverse Event: Identified in nature, severity, or frequency in the current protocol, informed consent, investigator brochure, or with other current risk information.
 2. Unexpected/Unanticipated Adverse Event: Not identified in nature, severity, or frequency in the current protocol, informed consent, investigator brochure, or with other current risk information.
 3. More Prevalent: Occurs more frequently than anticipated or at a higher prevalence than expected.
4. **Attribution.** Adverse events will be attributed to study participation according to these parameters:
 1. Unrelated: There is not a reasonable possibility that the adverse event may have been caused by participation in the study.
 2. Possibly Related: The adverse event may have been caused by participation in the study; however, there is insufficient information to determine the likelihood of this possibility.
 3. Related: There is a reasonable possibility that the adverse event may have been caused by participation in the study.
 4. Seriousness: Results in death, is life threatening, requires inpatient hospitalization or prolongs existing hospitalization, results in persistent or significant disability/incapacity, or any other event that may jeopardize the participant's health and may require medical or surgical intervention to prevent one of the other outcomes listed in this definition.
5. **Reporting.** Adverse events experienced by participants will be reported using the GSU IRB's password protected on-line adverse event reporting system, as follows:

IRB Reporting Requirements for Adverse Events

Internal Adverse Events. An internal adverse event is reportable if the occurrence meets all three of these conditions: 1) is unexpected, 2) is related or possibly related to participation in the research, and 3) is serious or places participants or others at greater risk of physical/psychological harm than was previously known or recognized. Internal adverse events are not reportable under these conditions: 1) expected and not more prevalent than expected, whether related or unrelated, and 2) unexpected and unrelated, regardless of seriousness, aside from death.

Internal Deaths. All internal deaths occurring during the conduct of the study or 30 days post-termination from protocol are required to be reported as adverse events even if they are expected or unrelated.

IRB Reporting Schedule for Adverse Events

For any unexpected and related or possibly related, serious or more prevalent event occurring during a research study, a report must be made through GSU's online reporting system as soon as possible but no later than 10 working days after the investigator first learns of the event. All other (expected adverse events) are reported as aggregate data at the time of IRB continuing review.

Report of Changes or Amendments to the Protocol

The annual DSM report will describe any minor actions or changes with respect to the protocol. In the unlikely event that major changes are required, [name] will discuss the needed changes with the NIDA Program Official first, reach a consensus agreement on the changes with the Program Official, and then provide a written description of the changes to NIDA.

A Data Safety and Monitoring Board (DSMB) will be led by [name], the Director of the Mark Chaffin Center for Health Development at GSU. [name] will serve as the Security Officer and will convene the DSMB quarterly to review and ensure the ongoing safety of the participants. With the help of [name], [name] will appoint other members of the DSMB who are not involved on the project prior to beginning the randomized pilot trial.

13. Confidentiality

Regarding data management and storage, all data will be collected using computerized self-report questionnaires. Only participants' study identification codes will be inputted computer-based databases. The codes that link the name of the participant and the study ID will be kept confidential in a secured cabinet or in a password-protected file on the encrypted GSU Enterprise Dropbox account, and then destroyed at the end of the study. The data will be imported directly into a password-protected SPSS data file stored on the GSU server. The server is protected by the GSU network, and a secured log-in is required from all users. In addition to these precautions, all personnel will have earned at least a bachelor's degree and have experience in conducting research. All research personnel collecting and manipulating data will have completed a Human Subjects Research Training and will meet weekly with the candidate to ensure strict compliance with the DSM plan. Only study personnel ([name], research staff, and mentorship team) will have access to data. No data will be released to other agencies unless participants consent to release. Audio recordings of therapy and data collection sessions will be used solely for research purposes.

Audio files will be stored on an encrypted hard drive at the research office, digital recordings will only be identified by numeric codes, and recordings will be destroyed at the end of the study. Only the candidate, project staff, and mentorship team will hear the content of the audio recordings.

14. References

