Technology-based brief assessments and prevention programs can revolutionize healthcare by allowing for low-cost, easily accessible, low-burden, effective prevention in healthcare settings without taking away from routine healthcare provided by physicians. It is essential that interventions target multiple health behaviors. This intervention focuses on several high-risk health behaviors among adolescents including substance use, SA, and SRBs, all of which are associated with both physical and mental health problems. This patient-oriented career development award would allow the candidate to pursue this line of research and ultimately develop, test, and disseminate effective technology-based prevention programs related to substance use, SA, and SRBs within primary care settings.

B. Developing an intervention for use by real-world providers. Adolescents prefer to be asked questions regarding substance use using technology-based or pencil paper modalities compared to physician-led assessments⁴⁸. Therefore, the development of a technology-based brief assessment and intervention would be an innovative method to provide services to patients with minimal added burden to providers. Further, this brief assessment and intervention will be informed by both providers and patients in community-based primary care settings, allowing for the specific needs of real-world providers to be addressed in the development of the intervention, thereby increasing the likelihood of dissemination and implementation ease.

C. Informing best practices for implementing assessment and prevention programs targeting SA and SRB in primary care settings. There is limited information in the assessment and prevention of SA and SRB among adolescents in primary care. The proposed research will not only provide feasibility and effect sizes for a future RCT to examine this intervention, it will also result in guidelines to implement substance-involved SA and SRBs within primary care settings guided by patient and provider preferences which could also inform other sensitive topics useful to assess in primary care settings.

4-2. Research Aims

A. Pilot Feasibility Trial

Participants: A total of 250 adolescents aged 14-18 will be recruited for a pilot feasibility trial. Adolescents will be screened using a screening assessment to determine if they are eligible for the study based on inclusion and exclusion criteria described below.

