Method: After their Well Check Visit with their pediatrician, adolescents will be recruited virtually or in-person to complete a screening survey about substance use. Participants who are ineligible to complete the study because they did not use substances or have friends that use substances in the past year will receive the recommended reinforcing message for abstaining from substance use such as “You’ve made a smart decision not to use alcohol or drugs” to reinforce choice (adapted from the Alcohol Screening and Brief Intervention for Youth⁶³). This “screening out” procedure will allow for adolescent substance non-use to be reinforced in the recommended manner to save time for providers by providing evidence-based care. Eligible participants (and their guardian) will be invited to meet with a research assistant either in person at the clinic, by phone, or in

a video conference meeting to discuss the research and obtain consent. While discussing informed consent, participants and their guardians will be informed of the sensitive nature of the prevention program and that the adolescent will complete the brief survey and then research procedures. Both the adolescent and guardian will be informed that if the adolescent discloses a SA history as a child that has not been previously reported to the appropriate officials (Department of Social Services or Law Enforcement depending on the perpetrator), a report will need to be made prior to the adolescent and guardian leaving the clinic. Both the adolescent and guardian will be informed that if the adolescent discloses imminent risk of suicide and the adolescent is not willing to agree to a safety plan, a mental health professional will need to conduct an exam to determine if hospitalization is needed.

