After consenting to the prevention program and completing the baseline survey, the adolescent will be randomized to receive the interactive online prevention program (15 minutes) or no intervention. All participants will then be contacted to complete 1-, 3-, and 6-month follow-up assessments. Participants will receive a \$5 gift card for screening for the study, \$30 gift card for completing the baseline survey up to the point of randomization (plus \$10 for completing the intervention if randomized to that condition), \$40 gift card for the 1-month follow-up, \$45 gift card for the 3-month, and \$50 gift card for the 6-month. Participants may also receive partial payment for the follow-up surveys based on the percentage of the survey they complete. They will also receive a \$5 bonus for completing each survey within a week of the date it was sent, and a \$10 bonus if they complete all the surveys. Additionally, participants randomized to the intervention group will receive an additional \$10.

The research team will observe restrictions imposed by Georgia State University and relevant government or public health authorities in the conduct of research activities.

5. Study Design

A. Organizational

The Principal Investigator of the overall study is [name] and is housed at Georgia State University (GSU). This study is funded by a NIDA career development award to GSU and all funds will go through GSU.

B. Setting and location:

Study procedures will take place at GSU and recruitment will occur at two sites: in the Old Fourth Ward Pediatrics clinic in Atlanta, Georgia and at the Medical College of Georgia-Augusta University Children's Hospital of Georgia in Augusta, Georgia.

Adolescents will either complete the consent, baseline survey, and intervention at their primary care clinic or they will complete those study activities online in a private location of their choosing. All participants will complete the follow-up surveys at 1 month, 3 months, and 6 months online in a private location of their choosing. When completing data surveys and/or the intervention remotely, we will ensure that they are in a private space in these ways:

- 1) displaying a reminder screen at the beginning of all surveys and the intervention that this should be completed in a private location
- 2) displaying a reminder screen to close the browser at the end

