Follow-up survey links will be sent via email, text, or social media (ex: Instagram) as preferred by the adolescent participant. The email used for follow-up survey correspondence is attached (see Email Script).

In addition to the survey links, research staff will encourage participation by sending brief, animated videos that relay the information in a more engaging format. These videos will contain information about survey length, study compensation, and what to expect for follow-up surveys.

Inclusion/exclusion criteria will be determined by the screening survey. Inclusion criteria for the pilot feasibility trial:

- 1) 14-18 years old
- 2) Attended a primary care visit for a preventative healthcare visit within the past month
- 3) Endorse self or friend substance use in the past year.

Exclusion criteria for the pilot feasibility trial:

The proposed prevention program will be made in English for the feasibility trial and requires that adolescents appropriately read and understand the program content. Therefore, it would be inappropriate for adolescents who are not able to read English. This is the same rationale for excluding adolescents with an intellectual or cognitive disability. Further, adolescents with intellectual/cognitive disabilities may have unique risk factors concerning sexual consent that will not be addressed in the prevention program. This is not to say that adolescents who do not speak English or who have intellectual disabilities are not at risk for substance use, SA, and SRBs, however, addressing these populations within the proposed research would not be possible. The screening questionnaire is written at less than a 6th grade reading level, so we believe people with intellectual/cognitive disability will be able to understand the question.

E. Informed Consent Process:

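### The substance-use ANOVA pools teens who use substances with non-users who only have a using friend, without adjusting or stratifying for own use; this costs precision and limits where the effect size can be applied

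*Combined protocol and SAP*

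**What the plan says.** Eligibility (section 5.D) requires a teen to "Endorse self or friend substance use in the past year". Section 4-2.A confirms how wide this is: the only teens screened out on this ground are those who "did not use substances or have friends that use substances in the past year". A non-user with a using friend therefore qualifies.

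Allocation (section 4-2.A) follows the baseline survey, when "the adolescent will be randomized to receive the interactive online prevention program (15 minutes) or no intervention". No ratio, method, stratification or quota is given.

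Analysis (section 10) disclaims efficacy conclusions because the sample is small. It then plans gender-by-treatment ANOVAs, which "will be conducted to determine if there are any preliminary effects on substance use, SA victimization, SA perpetration, and SRBs". Gender and condition are the only terms named. The section does not say whether the outcome is a post score, a change score or a repeated measure.

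Three other statements bear on the point:
- Section 4-1.C says the work will supply effect sizes for a later RCT.
- Section 3.B gives the program a dual aim of prevention and reduction.
- Section 12.A says substance use is assessed at every time point.

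The sample size has two readings. Section 4-2.A says "A total of 250 adolescents aged 14-18 will be recruited for a pilot feasibility trial"; section 10 says "Recruitment will be considered successful if 250 adolescents are screened and 70 meet criteria for the study".

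**The concern.** Own users can cut down. Friend-only non-users start at the floor and can only begin. These are different outcomes of a program meant both to prevent and to reduce use, and a single mean difference averages them with weights set by whatever user share happens to enrol.

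Own use is also likely to be a strong predictor of later use. Leaving it out of both allocation and model puts avoidable variance into the arm difference, and a chance excess of users in one arm moves the estimate. What is at stake is the preliminary substance-use effect size that the next trial is meant to draw on. The primary feasibility goal is not affected.

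**Working it through.** **No plan figure to reproduce.** The documents give no effect size, SD, alpha, power or user share for this analysis. What follows is an illustration.

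**Inputs from the documents.** 70 eligible (section 10), taken as 35 per arm; or 250 recruited (section 4-2.A), taken as 125 per arm. Equal, unstratified allocation is assumed because none is described.

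**Assumed inputs.** Control users average 6 days of use per month with SD 6; non-users stay at 0; post scores are compared; user share *q* = 50%, with 30% and 70% as a range. Where an effect is needed, the program lowers users' mean by 1.5 days.

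**Step 1: precision.** Total variance = *q*·36 + *q*(1−*q*)·36. The second term is the user mix, which adjusting for user status removes. SE = √(2·variance/*n* per arm).
- At *q* = 0.5, total variance is 18 + 9 = 27 and variance within user status is 18.
- 35 per arm: unadjusted √(54/35) = 1.24 days; adjusted √(36/35) = 1.01 days.
- User mix accounts for 9/27 = one third of the variance of the arm difference.

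| Per arm | User share | SE unadjusted | SE adjusted |
|---|---|---|---|
| 35 | 30% | 1.02 | 0.79 |
| 35 | 50% | 1.24 | 1.01 |
| 35 | 70% | 1.37 | 1.20 |
| 125 | 50% | 0.66 | 0.54 |

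These SEs use the control-arm variance in both arms. If treated users really average 4.5 days, the treated-arm variance is 18 + 0.25·4.5² = 23.06 and the unadjusted SE is √((27 + 23.06)/35) = 1.20, so the gain is slightly smaller.

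**Step 2: chance imbalance.** Let the number of users in each arm be Binomial(*n*, 0.5).
- 35 per arm: P(arms differ by 6 or more users, 6/35 = 17 points) = 0.188.
- 125 per arm: P(differ by 22 or more, the first whole number above 17.1 points) = 0.006.

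On post scores, a 6-user imbalance with 35 per arm shifts the difference by 6/35 × 6 = 1.03 days.

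**Step 3: what the pooled figure measures.** If non-users do not change, the pooled effect is *q* × 1.5 days: 0.45, 0.75 and 1.05 days at 30%, 50% and 70% users. At 50% the standardised effect is 0.75/√27 = 0.14, against 1.5/6 = 0.25 in users alone.

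**Step 4: bias.** 20,000 simulated trials were run with 70 participants, 50% users, control users 1 SD above non-users and a 0.5 SD effect in users. The true pooled effect is 0.5 × −0.5 = −0.25. The mean estimate was −0.25 with and without user status in the model; the SD of the estimate was 0.174 with it and 0.194 without.

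**Step 5: users alone.** With 17.5 users per arm, SE = √(2·36/17.5) = 2.03 days, larger than the assumed 1.5-day effect.

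**The case against.** A reader might infer that the planned estimate is biased toward zero. The documents do not support that. Section 10 does not name the effect in users as its target, section 3.B makes prevention an aim, and section 4-2.A admits friend-only teens on purpose. For that mixed population the randomised difference is unbiased, as step 4 shows. It is diluted only as a measure of the effect in users, and only if non-users change less.

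A reader might also infer that imbalance in user share would dominate the result. Even on the assumed values it is one third of the variance; the rest is noise among users, and after adjustment the SE of 1.01 days still exceeds the 0.75-day pooled effect. The 1.03-day shift also needs a post-score comparison. On change scores, with control users stable on average, it disappears, and section 10 leaves the outcome form open.

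Further points on the plan's side:
- The analysis is secondary, with no efficacy conclusions planned.
- Substance use is one of four outcome domains, and the floor argument is not made here for the others.
- A later trial with the same eligibility and a similar mix could use the pooled estimate.
- The survey instruments are not in the documents, and the criterion is worded jointly, so it is not certain that screening records own use separately.

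All of this stands and limits the point. It does not explain leaving baseline use out of the model. The small-sample caveat concerns size; a larger sample would not show whose effect had been estimated.

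**Conclusion.** The point holds as one about precision and interpretation. The plan mixes own users with friend-only non-users and takes no account of own or baseline use in allocation, model or reporting, although substance use is assessed before randomisation.

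On the assumed values with 35 per arm, the avoidable loss is roughly a fifth of the standard error (1.24 to 1.01 days), and a user-share gap of 17 points or more arises about one time in five. With 125 per arm such a gap is rare, but the proportional loss of precision is the same. The sizes rest on assumed means, SD, user share and post-score analysis.

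Understatement of the effect in users is conditional on non-users changing less. The floor makes that plausible, but the documents give neither a user share nor an effect by user status. The consequence is confined to the preliminary substance-use effect size; the change is worth making because that figure is promised to a future RCT and the adjustment costs almost nothing.

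**What to change.** 1. In section 10, add to the substance-use model own past-year use (yes/no) and the baseline value of the outcome, both taken before randomisation. State whether the outcome is a post score, a change score or a repeated measure.
2. Preferably also stratify allocation by own use, where it is known in time. Confirm that the screening or baseline survey records own use separately from friends' use.
3. Report the user share by arm. As descriptive results with confidence intervals, report the arm difference among own users and counts of new use among non-users.
4. Reconcile the 250 recruited in section 4-2.A with the 250 screened and 70 eligible in section 10, since exposure to imbalance depends on which applies.

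The cost is one stratum in the randomiser, two model terms and a few table rows; no extra participants or visits are needed. The downside is that the separate estimates will be very imprecise at about 70 participants (SE about 2 days among users in the illustration). They should not drive conclusions or, on their own, set the size of the next trial.
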